6.0 Data and Specimen Banking

- 6.1 Storage and Access: Storage and Access: De-identified neuroimaging data will be stored locally on servers supported by the Center for Magnetic Resonance (CMRR). De-identified cognitive and behavioral data will be stored in a secure, HIPAA-compliant RedCap database supported by the university of Minnesota.
- 6.2 Data: Data elements to be stored will include processed, de-identified neuroimaging results (ex. regional brain volumes, measures of white matter integrity, and measures of brain connectivity), de-identified neurocognitive test results, and de-identified behavioral questionnaire data.
- 6.3 Release/Sharing: Release/Sharing: There are no plans to share these data with outside entities.

7.0 Sharing of Results with Participants

7.1 Standardized neurocognitive test results may be shared with participants' parents if requested. [name] is a clinical neuropsychologist with 20 years of experience providing clinical neuropsychological information to parents. This will be done in an ethical manner, sharing only the necessary data and not interpreting it clinically but, rather, passing on standardized scores in a manner consistent with American Psychological Association ethical standards. Neuroimaging results are not shared with participants with the exception of a single "souvenir image". If a potential abnormality is identified in the MRI scan and the radiologist review indicates that a clinical follow-up is needed, a full set of images will be prepared on a DVD for sharing with the clinician doing the follow-up.

8.0 Study Duration

- 8.1 Describe:
 - Participants will complete the 6 visits described above, typically within a span of 8 weeks maximum.
 - All study participants will be enrolled within the two year timeframe of the study.
 - Data analysis is expected to continue for 1-2 years post study conclusion.

9.0 Study Population

- 9.1 Inclusion Criteria:
 - Documented heavy prenatal alcohol exposure (self-report, social service records, or adoption records) and meeting criteria for an associated FASD diagnosis (FAS, partial FAS, or ARND).
 - An available parent or legal guardian capable of giving informed consent
- 9.2 Exclusion Criteria:
 - All participants: Substance abuse in the participant; Neurological condition or other developmental disorder; Serious psychiatric disorder known to effect brain functioning and cognitive performance; Birthweight < 1500 grams; MRI contraindication, tDCS contraindication.
- *9.3* Screening: Participants will be screened by telephone using the attached screening tool.

10.0 Vulnerable Populations

- 10.1 Vulnerable Populations:
 - \boxtimes Children
 - □ Pregnant women/Fetuses/Neonates
 - \Box Prisoners
 - □ Adults lacking capacity to consent and/or adults with diminished capacity to consent, including, but not limited to, those with acute medical conditions, psychiatric disorders, neurologic disorders, developmental disorders, and behavioral disorders
 - □ Approached for participation in research during a stressful situation such as emergency room setting, childbirth (labor), etc.
 - □ Disadvantaged in the distribution of social goods and services such as income, housing, or healthcare
 - □ Serious health condition for which there are no satisfactory standard treatments
 - □ Fear of negative consequences for not participating in the research (e.g. institutionalization, deportation, disclosure of stigmatizing behavior)
 - □ Any other circumstance/dynamic that could increase vulnerability to coercion or exploitation that might influence consent to research or decision to continue in research
 - \Box Undervalued or disenfranchised social group
 - \Box Members of the military
 - \Box Non-English speakers
 - \Box Those unable to read (illiterate)
 - \Box Employees of the researcher
 - \Box Students of the researcher
 - \Box None of the above
- 10.2 Adults lacking capacity to consent and/or adults with diminished capacity to consent:
 - N/A
- 10.3 Additional Safeguards:
 - Children and adolescents are the focus of this study because it is a study of the neurodevelopmental effects of prenatal alcohol exposure and the desired outcome is to learn more about the presentation of effects over the course of development. Children and adolescents will all undergo a formal assent process at the same time as the parent undergoes a formal informed consent process. Children who are wards of the state will not be enrolled.

11.0 Local Number of Participants

11.1 Local Number of Participants to be Consented: Up to 60 participants will be consented in this study, with the goal of having 40 participants enroll and complete the full study.

12.0 Local Recruitment Methods

- 12.1 Recruitment Process: Families of potential participants will be contacted by research staff or will initiate contact themselves. Visitors to the clinics described below may see flyers and brochures describing the study at the time of their clinic appointment although they will not be recruited directly by their clinician. Mailings will also be sent to families of children with FASD via lists provided by the Minnesota Organization on Fetal Alcohol Syndrome (MOFAS). MOFAS has close working relationships with [name], [name], [name], [name] and both clinics. All recruitment materials will be submitted for IRB approval upon development, before use in the study. Telephone scripts will be utilized.
- 12.2 Source of Participants: Participants will be recruited from two University of Minnesota Medical Center Clinics in which co-investigators see patients: The Fetal Alcohol Spectrum Disorders clinic ([name], Ph.D., [name], Ph.D) and the International Adoption Clinic (directed by [name], M.D.).
- 12.3 Identification of Potential Participants: Potential participants will selfidentify in some cases based on advertisements. In other cases, participants will be recruited based on having been seen for an evaluation for FASD. Participants will not be recruited by a clinician (to avoid potential coercion and/or confusion about clinical care vs. research. Instead, research staff will contact families and will conduct telephone screens to determine eligibility. Access to contact information for potential participants will be obtained from the clinicians who are co-investigators on the study ([name], [name], and [name]). Patients who "opted out" of allowing their clinical data to be utilized for research via the standard UMMC / Fairview clinical consent form will not be recruited.
- 12.4 Recruitment Materials: See attached recruitment materials in ETHOS.
- 12.5 Payment: Participant families will receive payment (check or pre-paid card) for participation. Because the participants are children, the payment will be provided to the parent on behalf of the child. Payment will be made at the completion of the study (final visit) or at the time of a participant dropping out of the study. Payment will be based on procedures attempted and/or completed as follows:
 - \$50 for the neuropsychological testing and parent rating forms
 - \$50 for each MRI scan (\$100 total)
 - \$25 for each tDCS session (\$125 total)

• The maximum payment per participant will be \$275.

13.0 Withdrawal of Participants

- 13.1 Withdrawal Circumstances: Participants may withdraw or be withdrawn from the study at any point. Participants may be withdrawn for MRI contraindications (ex. metal implanted in body between visit 1 and 2), tDCS contraindications (ex. seizures, brain trauma), failure to complete study procedures, or loss to follow-up.
- *13.2* Withdrawal Procedures: Participants who withdraw or are withdrawn from the study will not be followed further. Payment will be provided for all attempted and/or completed procedures.
- *13.3* Termination Procedures: Data collected prior to withdrawal may be used from withdrawn participants.

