1.0 Objectives

- 1.1 Purpose:
 - Aim 1: Characterize the feasibility and tolerability of combined cognitive remediation and tDCS in children ages 10-16 with FASD.
 - Hypothesis 1: Children with FASD will tolerate the procedures and remain in the study with less than 20% dropout over the course of cognitive remediation and tDCS
 - Aim 2: Evaluate the potential additive benefits of tDCS to the base cognitive remediation program.
 - Hypothesis 2: Cognitive remediation with active tDCS vs. sham tDCS will result in greater gains over the courses of treatment.
 - Aim 3: Examine the brain circuitry changes following the intervention.
 - Resting and task fMRI will demonstrate greater change with active compared with sham tDCS.

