3.0 Study Endpoints/Events/Outcomes

3.1 Primary Endpoint/Event/Outcome:

The primary endpoints will be BrainHQ (Posit Science, San Francisco, CA) task performance measures.

- Learning curves derived from repeated sessions of BrainHQ training will serve as the primary endpoints:
 - Scene Crasher; Mind Bender; Juggle Factor; Eye for Detail; and Divided Attention
- *3.2* Secondary Endpoint(s)/Event(s)/Outcome(s):
 - Neurocognitive measures will be administered at baseline and again after completion of training:
 - Subtests from the Delis-Kaplan Executive Functioning System (DKEFS)
 - Delis Rating of Executive Functioning (D-REF)
 - NIH Toolbox measures (Flanker, Dimensional Card Sort Test, Picture Sequence Memory Test, and Oral Symbol Digit Test)
 - Functional Connectivity analysis of resting-state fMRI data
 - o Seed-based functional connectivity measure
 - Graph theoretical analysis of connectivity

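### An MRI contraindication can end a child's whole participation, although only Aim 3 needs MRI, and the plan does not say whether such a loss counts toward the 20% dropout limit

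*Combined protocol and SAP*

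**What the plan says.** **Withdrawal.** Section 13.1 states: "Participants may be withdrawn for MRI contraindications (ex. metal implanted in body between visit 1 and 2"). It lists tDCS contraindications separately, along with not completing procedures and loss to follow-up. Section 13.2 adds: "Participants who withdraw or are withdrawn from the study will not be followed further". Section 13.3 allows partial use of the data: "Data collected prior to withdrawal may be used from withdrawn participants". No section provides for stopping MRI alone.

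**Feasibility.** Aim 1 (section 1.1) is to "Characterize the feasibility and tolerability of combined cognitive remediation and tDCS in children ages 10-16 with FASD". Hypothesis 1 expects that children will tolerate the procedures and "remain in the study with less than 20% dropout over the course of cognitive remediation and tDCS". Dropout is not defined by cause.

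**What needs a scan.** Imaging belongs to Aim 3: "Resting and task fMRI will demonstrate greater change with active compared with sham tDCS". It also supplies the connectivity endpoints among the secondaries in section 3.2. The primary endpoints need no scan: "Learning curves derived from repeated sessions of BrainHQ training will serve as the primary endpoints". Nor do the cognitive secondaries, which are tested at baseline and after training.

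**Schedule (section 5.2).** Scans are at Visit 1, before the first stimulation session, and at Visit 6, after the last. Training sessions are at Visits 1 to 5. Section 5.3 adds a symptom call 30 days after the last session.

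**The concern.** A reason that affects only the third aim can end data collection for all three. In section 13.1's own example the contraindication arises after Visit 1, when four of the five training sessions are still to come and no scan is due until Visit 6. If the child is withdrawn, section 13.2 stops the collection of data that do not depend on the scanner.

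The feasibility result is exposed as well. Aim 1 concerns remediation plus tDCS, but Hypothesis 1 is worded as remaining in the study. A child withdrawn for an MRI reason during training has not remained in it, so the natural reading counts that child as dropout. The pilot could then miss its feasibility criterion, or look less feasible, because of events that say nothing about whether children tolerate remediation and tDCS.

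**Working it through.** **1. The plan's own power figure.** Section 16.2 gives n=20, alpha 0.05, power 0.8 and a detectable effect of 0.9. Taking n as per arm (section 5.1) and a two-sided test, an effect of 0.9 has power 0.812 by the normal approximation and 0.792 by the noncentral t. The figure reproduces.

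**2. Data lost, by timing.** There are five training sessions, at Visits 1 to 5. A child withdrawn after Visit k loses 5 − k of them.

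| Withdrawn | BrainHQ sessions lost | Visit 6 cognitive tests | 30-day call (13.2 read literally) |
|---|---|---|---|
| After Visit 1 | 5 − 1 = 4 | lost | lost |
| After Visit 3 | 5 − 3 = 2 | lost | lost |
| At Visit 6, before testing | 0 | lost | lost |

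For pre-post outcomes, if lost children are not replaced, power at an effect of 0.9 (two-sided t) falls from 0.792 with 20 per arm to 0.770 with 19 and 0.746 with 18.

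**3. The dropout limit.** With 40 children:
- 7/40 = 17.5%, which passes
- 8/40 = 20.0%, which is not below 20% and fails
- each further child counted adds 1/40 = 2.5 percentage points

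**4. Effect of counting MRI losses.** The protocol gives no rate for either kind of loss, so both are assumptions. Let b be the probability of dropout for non-MRI reasons and m the probability of an MRI-related loss, taken as independent. If both count,

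p = 1 − (1 − b)(1 − m), and the chance of meeting the limit is P(X ≤ 7) with X ~ Binomial(40, p).

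For b = 10%:
- m = 0: p = 0.10, chance 0.958
- m = 2.5%: p = 1 − 0.90 × 0.975 = 0.1225, chance 0.891
- m = 5%: p = 1 − 0.90 × 0.95 = 0.145, chance 0.784
- m = 10%: p = 1 − 0.90 × 0.90 = 0.19, chance 0.501

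The range over b:

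| Non-MRI dropout b | MRI losses not counted | m = 2.5% | m = 5% | m = 10% |
|---|---|---|---|---|
| 5% | 0.999 | 0.992 | 0.963 | 0.784 |
| 10% | 0.958 | 0.891 | 0.784 | 0.501 |
| 15% | 0.756 | 0.624 | 0.485 | 0.245 |

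**5. The denominator.** Section 5.1 randomizes 20 per arm, whereas section 11.1 consents up to 60 and aims for 40 completers. If recruitment runs until 40 complete, the base is larger: 9/49 = 18.4% passes and 10/50 = 20.0% fails. The figures in steps 3 and 4 use a fixed 40.

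**The case against.** The strongest reply is that the rule is narrow and that its effect on the feasibility result is inferred. Much of this stands:

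- **Withdrawal is discretionary.** Section 13.1 says children *may* be withdrawn. A reader might infer automatic removal, but the text does not say so. Nor does it say that one failed or refused scan ends participation; section 12.5 pays for procedures that were only attempted.
- **Counting MRI losses as dropout is not an explicit rule.** A reader might infer that they are certainly counted. Hypothesis 1 refers to the course of remediation and tDCS, which could be read to leave out a loss first arising at Visit 6.
- **The primary data are not always affected.** The baseline scan precedes the first stimulation session, and a child lost at Visit 6 has complete learning curves. Section 13.3 lets earlier data be used. Losing four of five sessions is the worst case for a child who has begun training.
- **Exclusion at screening is a different matter.** Section 9.2 bars children with "MRI contraindication, tDCS contraindication". A reader might add them to the dropout problem, but they never enrol and cannot drop out. Requiring children who can be scanned is a coherent choice in a trial with an imaging aim; its cost is in generalizability.
- **Replacement may protect power.** Consenting up to 60 could restore the number of completers.

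These points limit how often the problem arises and how large it is. They do not remove it. Section 13.1 names the MRI ground, section 13.2 ends follow-up, no MRI-only route exists, and replacement does not settle how dropout is counted.

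**Conclusion.** The concern holds in this form: the plan does not separate stopping MRI from leaving the study, and it does not say whether MRI-related withdrawals count toward the dropout limit. Whenever the rule in section 13.1 is used, non-MRI data after that point are lost: up to four of five primary-endpoint sessions for a child already in training, plus the Visit 6 cognitive tests and the 30-day call.

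The effect on Hypothesis 1 is conditional. If MRI losses are counted, and if non-MRI dropout is 10% among 40 children with independent causes, MRI losses of 2.5% to 10% lower the chance of meeting the limit from 0.958 to between 0.891 and 0.501. The true rates cannot be known from the protocol. The documents do not support saying that the feasibility result will fail for this reason, or that the section 9.2 exclusion is an error. This is a cheap improvement worth making before enrolment.

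**What to change.** 1. **Sections 13.1 and 13.2.** Separate discontinuation of MRI from withdrawal from the study. An MRI-only reason ends the remaining scans but not the collection of non-MRI outcomes. Whether stimulation continues is for the sponsor to decide under the separately listed tDCS criterion; this is not a proposal on that question.
2. **Section 13.1 and the schedule.** The example places the event between Visits 1 and 2, while section 5.2 puts the scans at Visits 1 and 6. The sponsor should reconcile the two.
3. **Hypothesis 1.** Count dropout as discontinuation of remediation or tDCS, state the denominator, and report MRI-only losses separately with the all-cause figure alongside.

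No change to section 9.2 is asked for.

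**Cost.** This is protocol wording. If withdrawn children would have been replaced from the up to 60 consented, each unscanned child kept among the 40 costs Aim 3 one paired scan. If they would not have been replaced, Aim 3 loses nothing, because the child gives no second scan under either rule.

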 - d. NIH Toolbox Oral Symbol Digit Test (OSDT) is a measure of processing speed. (Denboer, Nicholls, Corte, & Chestnut, 2014).
 - The following additional assessments will be administered to the child:
 - a. Subtests from the Delis-Kaplan Executive Functioning System (DKEFS): a standardized battery of executive functioning.
 - The following questionnaires will be administered to the parent:
 - a. Parent and Child Questionnaire
 - b. Behavior Assessment System for Children 3nd
 Edition (BASC-3): a standardized parent-report questionnaire of typical and atypical child behavior.
 - c. Delis Rating of Executive Functioning (D-REF): a standardized parent-report questionnaire of child planning, organization, attention, inhibition, and emotional control.
 - The tDCS Report of Symptoms questionnaire will be administered to the child before and after each tDCS/sham intervention:

- a. Assessment tool to monitor for common, specific side effects noted across many existing tDCS studies, including but not limited to itching, prickling, burning sensation, nausea, fatigue and headache.
- b. Approximately 3-5 minutes to administer and is typically performed twice during each intervention session (once before and once after the session).
- c. Furthermore, participants will be continuously monitored by a member of the study staff throughout each intervention session to ensure comfort and safety.
- d. In addition, at the end of each intervention visit, the subject will be asked if they think they received the active or sham condition.
- All forms are attached to this submission

5.3 Follow-Up: Participants will be contacted by phone 30 days after the last intervention session. The tDCS Report of Symptoms questionnaire will be administered.

- 5.4 Individually Identifiable Health Information: See attached HIPCO Ancillary Review Form and HIPAA Authorization form
- 5.5 Use of radiation: NA neither MRI nor tDCS uses ionizing radiation
- 5.6 Use of Center for Magnetic Resonance Research: This study uses the CMRR and follows all CMRR protocols and procedures.

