- Criteria for discontinuation that may rarely occur are sores at the tDCS administration site, and headaches that temporarily affect comfort / functioning.
- Mild side effects that typically resolve upon discontinuation of tDCS include light itching under the electrode at the beginning of administration, headache, fatigue, and nausea.
- The participant may also choose to discontinue stimulation at any time during the session if experiencing discomfort or side effects.
- No other risks are anticipated. Nonetheless, in order to minimize risks, study staff will be using standards of administration that have been shown to be safe in numerous other studies and across more than 2000 studies (Liebetanz et al., 2009; Nitsche et al., 2007; Poreisz, Boros, Antal, & Paulus, 2007) using tDCS; this includes length of administration, magnitude of the current, size of electrode sponges used, and method of applying stimulation.
- Any unanticipated problems or adverse events will be reported to the IRB

The risks of neurocognitive testing / checklists are as follows:

- Neurocognitive testing can be challenging and tiring. Children will be given ample opportunities for breaks and will be given encouragement to complete tasks to the best of their ability.
- Checklists cover sensitive topics. Participants have the option of skipping items that they are uncomfortable answering.

- 14.2 Reproduction Risks: There are no known risks to fetuses from MRI, but we will take steps to ensure that no pregnancies are exposed to MRI nonetheless. Parents and participants will be told that the participant should not undergo MRI if there is a pregnancy or the possibility of a pregnancy (i.e. sexual intercourse without effective contraception taking place). There are no known risks to fetuses from tDCS, but we will similarly take steps to ensure that no pregnancies are exposed to tDCS.
- 14.3 Risks to Others: Parents who accompany children to the MRI facility (CMRR) will be screened as though they will be entering the MRI suite (even though the plan will be for them to remain in the attached control room). All CMRR procedures will be followed in this regard.

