18.0 Provisions to Monitor the Data to Ensure the Safety of Participants

N/A - The principal investigator will monitor safety and data quality for this study. They will ensure that adverse events are reported accordingly and that data are generated, documented (recorded), and reported - in compliance with this protocol, with Good Clinical Practice, and any other applicable regulatory requirements.

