20.0 Compensation for Research-Related Injury

- 20.1 Compensation for Research-Related Injury: Compensation for Research-Related Injury: In the event that this research study results in an injury, we will provide treatment including first aid, emergency care, and follow-up as needed. Care for injuries would be billed in the ordinary manner and costs would not be covered by the research study itself.
- 20.2 Contract Language: N/A

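### Section 13.2 ends follow-up for every withdrawn child, which cancels the 30-day symptom call that Section 5.3 schedules without exception

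*Combined protocol and SAP*

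**What the plan says.** Section 13.2 gives one rule for every kind of withdrawal: "Participants who withdraw or are withdrawn from the study will not be followed further". Section 13.1 shows that this reaches children removed by the team as well as families who choose to leave: "Participants may be withdrawn for MRI contraindications (ex. metal implanted in body between visit 1 and 2), tDCS contraindications (ex. seizures, brain trauma"). It also lists failure to complete procedures and loss to follow-up. Section 13.3 sets out what is kept: "Data collected prior to withdrawal may be used from withdrawn participants".

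Section 5.3 says: "Participants will be contacted by phone 30 days after the last intervention session". The tDCS Report of Symptoms is given on that call. The text is not limited to children who finish the course, and its clock starts at the last session, which an early leaver also has.

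Section 5.2 has the same questionnaire completed before and after each session. It places Visit 6 (repeat MRI and 60 minutes of cognitive testing) within a week of the last session and lists no symptom questionnaire there. Section 3.2 makes the cognitive tests and the parent-rated D-REF secondary endpoints, measured at baseline and once training is complete.

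**The concern.** Aim 1 is to describe feasibility and tolerability in children. For a child who stops early, the 30-day call is the only planned record of symptoms after the last session. Under 13.2 that record is not made, even when the team made the decision and the family would gladly take a call. The report on later symptoms would then describe only children who stayed in the study.

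Staff also cannot tell from the protocol whether to call a withdrawn child, because neither section refers to the other.

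There is a smaller, related loss. Nothing separates being unable to have an MRI from leaving the study. A child who has finished all five training sessions and then becomes ineligible for the scanner could be withdrawn and lose the cognitive tests and D-REF, which need no scanner.

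**Working it through.** The plan gives no figure for this point. Its one power statement (Section 16.2: 20 per arm, effect size 0.9, power 0.8) reproduces, with two-sided t-test power of 0.792 and normal-approximation power of 0.812, and it is not in question here. The check is a comparison of sections, followed by a count.

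**What a withdrawn child loses and keeps**

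| Item | Source | After withdrawal under 13.2 |
|---|---|---|
| Symptom reports at attended sessions | 5.2, 13.3 | Kept |
| BrainHQ data from attended sessions | 3.1, 13.3 | Kept |
| Counting as a dropout | 1.1 | Kept |
| Care for a research injury | 20.1 | Kept |
| Adverse-event reporting and safety monitoring | 14.1, 18.0 | Kept |
| 30-day symptom call | 5.3 | Lost if withdrawn before the call |
| Visit 6 cognitive tests and D-REF, as endpoints | 3.2, 5.2 | Lost only if withdrawn after session five and before Visit 6 |

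The last row is narrow because 3.2 measures these endpoints once training is complete. A child who stops part-way does not reach that point.

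**How many children could lack the call**

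Inputs: dropout below 20% (Hypothesis 1, Section 1.1); 40 randomised, 20 per arm (5.1); a goal of 40 who complete, with up to 60 consented (11.1).

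- If 40 are randomised, the largest count strictly below 20% is 7, since 7/40 = 17.5% and 8/40 = 20.0%.
- If 40 must complete out of N, then (N − 40)/N < 0.20 gives N < 50. So N is at most 49, with 49 − 40 = 9 dropouts and 9/49 = 18.4%.

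These are ceilings. They count all dropouts in both arms, and include families who refuse contact or cannot be found, for whom no wording would help. They also treat every withdrawal before the call as a dropout under Hypothesis 1. That hypothesis is worded for the training course, so a child withdrawn after session five might have to be added.

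**The case against.** The strongest reply is that there is no contradiction. Section 5.3 is the general schedule and 13.2 is the specific rule for children who leave. That reading is reasonable and may be what was intended. It removes the conflict but not the loss, because the call is still not made. The consent pages are not in the copy reviewed, and they may say something about contact after withdrawal.

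A second reply is that little depends on the call. The only numerical criterion for Aim 1 is the dropout rate, which 13.2 leaves untouched. The symptom questionnaire is not listed as an endpoint in 3.1 or 3.2. Section 14.1 expects mild effects to resolve once stimulation stops. All of this stands, and it keeps the point small. But tolerability is part of Aim 1, and the plan thought later symptoms worth asking about.

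Several stronger readings are tempting, and the documents do not support them:

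- *Children who leave after harm are abandoned.* Section 20.1 promises "treatment including first aid, emergency care, and follow-up as needed" for research injury. Section 14.1 says "Any unanticipated problems or adverse events will be reported to the IRB", and Section 18.0 says "The principal investigator will monitor safety and data quality for this study". What these sections do not do is schedule a symptom contact.
- *Any child who stops a stimulation block loses follow-up.* Section 14.1 says "The participant may also choose to discontinue stimulation at any time during the session if experiencing discomfort or side effects", but does not call this withdrawal. Section 13.1 is permissive, so only children actually withdrawn are affected.
- *Every early leaver loses a secondary endpoint and should be tested on leaving.* The definition in 3.2 rules out the first part. On the second, visits may spread over as much as 8 weeks (8.1), so a one-week window after the last session could close before staff know the child has stopped. A child who leaves after Visit 1 would be retested within days of baseline. Such scores could not simply be pooled with those of children who finished.
- *The comparison of arms at Visit 6 is biased.* No section gives reasons for leaving by arm, so this is speculation. Any such bias is likely small beside a standard error of √(2/20) = 0.32 SD.

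**Conclusion.** The point holds as a cheap improvement of modest weight. Section 13.2 as written removes the only symptom report planned after the last session for children who leave early, and it sits unreconciled with 5.3. If dropout meets the plan's own hypothesis, the call would be missing for at most 7 of 40 children (17.5%) or 9 of 49 (18.4%). The avoidable share is smaller and cannot be worked out, because the documents say nothing about why children would leave or how many families would still take a call. The percentages are shares of children without the call. They are not symptom rates, and they do not describe the active arm alone.

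The loss of Visit 6 tests is confined to children who finish all five sessions and are withdrawn before that visit. The documents give no basis for counting them.

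**What to change.** - Reword 13.1 and 13.2 so that stopping study procedures and declining further contact are separate events, and make 5.3 agree.
- Make the 5.3 call, 30 days after the last session attended, to every child whose family does not decline contact. Report how many early leavers were reached, by arm.
- State that an MRI contraindication alone cancels the scan but not the Visit 6 cognitive tests and D-REF for a child who has completed all five training sessions.

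Whether stimulation sessions continue for a child who can no longer be scanned is for the sponsor to decide. No further BrainHQ data are expected, since that training is given only within the sessions.

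The cost is a change to protocol and consent or assent wording with IRB review, including a check against Section 12.5, which pays families when they drop out. After that it is one call per early leaver, with a questionnaire of about 3 to 5 minutes, for at most 7 to 9 families if the dropout hypothesis holds. For a child covered by the third change, it is the 60 minutes of testing and the D-REF already planned. The drawbacks are a small burden on families who have chosen to stop, and contact that will remain incomplete.
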